8.5 Extra Data

The protocol calls for certain procedures only on specified days (e.g. coagulation panels including D-dimer on Days 1, 3, 5, 7, 9, 11, 13, and 14) but allows for collection on other days when ordered by the clinician. We choose to include these ad hoc data in all analyses, because the frequency of sampling the time scale of change in response variables is anticipated to be long compared to sampling, and clinician-ordered sampling should not introduce sizeable bias.

8.6 Interim Analyses and Data Monitoring

8.6.1 Safety Review

The analysis plan includes interim review by the DSMB for the purpose of monitoring study conduct and assessing participant safety after 50% of patients have completed the study or 10 deaths have occurred (whichever happens first). This review includes the number, proportion, and listing of participants with SAEs (including segregation of those involving deaths), treatment-emergent AEs, and discontinuation of study medication due to AEs. These presentations are descriptive, with no formal inferential methods used. No specific rules for halting study enrollment or study interventions for safety are specified; however, the DSMB may request formal inferential testing to assess the risk-benefit profile of these study medications in this study population.

8.6.2.2 Primary Hierarchical Composite Endpoint

We conduct an interim analysis of the efficacy with respect to the hierarchical composite endpoint using data as December 31, 2020. This analysis was added to the protocol at the December 15, 2020 DSMB meeting to assess whether there may be evidence of treatment differences in clinical outcomes.

The analysis uses the win ratio, a modification of the Mann-Whitney U-statistic (Pocock et al., 2012; Finkelstein and Schoenfeld, 2018). A description of the win ratio algorithm is provided in Section 9.2.1 and Table 3. We calculate U-statistics by comparing all possible pairs of treatment-vs-placebo

patients according to the win ratio algorithm. This generates a summary U-statistic for each patient and estimates the win ratio — the proportion of comparisons ‘won’ by dipyridamole patients. We obtain confidence intervals for the win ratio by bootstrapping the data in-hand and spending only the α for Type I error that remains from the D-dimer analysis according to the Lan-DeMets spending function.

To decide futility or benefit, we apply conditional power (Lan and Trost, 1999; Siu and Lan, 2001; Lachin, 2006). This approach is advantageous, because it does not require an adjustment for the Type I error nor an adjustment on the final critical value to claim significance. Our calculations of conditional power (CP) are based on the estimated effect at the time of analysis for a total sample size of $N = 127$ (based on win ratio sample size calculations in Yosef et al., 2019):

$$CP = \Pr(\text{reject } H_0 \text{ at the end of the study} \mid \text{interim data, estimated effect size is unbiased}).$$

The decision to proceed with the trial depends on the value of CP as follows:

1. $CP < 0.3$: Stop for futility
2. If $0.3 \leq CP < 0.8$: Continue the trial but re-estimate sample size up to $N = 160$
3. If $0.8 \leq CP < 0.9$: Continue the trial with $N = 127$
4. $CP \geq 0.9$: Stop for benefit

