PLANNED INTERIM ANALYSES	
Interim data analyses will be performed and study conduct reviewed by the DSMB at the specified milestones when the following number of participants have completed the study:
 
 1. Safety and futility will be evaluated after approximately 25% and 50% of participants have completed the study or 10 deaths have occurred (whichever occurs first), 2. Study conduct will be evaluated after approximately 25% and 50% of participants have completed the study, or three months after initiation of enrollment (whichever comes first). 3. Efficacy will be evaluated when 50% of participants have completed the study. 4. A second efficacy analysis will occur for clinical outcomes pursuant to the December 2020 DSMB meeting. 
The first efficacy endpoint will be the proportion of patients by treatment group whose change in D-dimer levels is at least +5% as estimated by simple linear regression. The efficacy analysis will use the O'Brien-Fleming method to correct for interim analyses. For the futility endpoint, if the lower limit for the 95% confidence interval of the daily change in D-dimer is above 9% at the time of the 50% interim analysis, the trial will be stopped. The second efficacy endpoint will be a hierarchical composite outcome of time to death, days on ventilation, change in SpO₂/FiO₂ ratio, and Ordinal scores. It will be analyzed using nonparametric win ratio analysis (Pocock et al., 2012). Decisions regarding the secondary endpoint will be based on conditional power, which does not require adjustments for Type I error (Lan and Trost, 1999; Siu and Lan, 2001; Lachin, 2006).
 
Serious adverse events will be monitored by the committee on an ongoing basis throughout the study.

[figure not shown]

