The win proportion is the probability that a treatment patient experiences better outcomes when compared to a placebo patient, thus representing the effect size. The analysis is powered to a 0.67 win proportion. For the efficacy endpoint using the O'Brien-Fleming method to correct for interim analyses, we will use a P value cutoff of 0.006 for the midway point analysis and 0.044 for the final analysis, yielding an overall alpha (type I error rate) of 0.05.

15.3.1 *Interim Analyses of Primary Endpoints*

When approximately 25% and 50% of participants have completed the study or 10 deaths have occurred (whichever occurs first), an interim analysis for safety and futility will be conducted by the DSMB. The interim analyses for efficacy will be limited to the review after 50% of participants have completed the study to limit the cost to power from multiple interim analyses.

The interim analysis of benefit for the primary endpoint will be conducted on a binary version of patient-level D-dimer change rates. Rates will be estimated separately for each patient by simple linear regression and dichotomized by whether the rates was above a 5% daily increase.

Treatment groups will be compared by a Fisher's exact test. We will use the O'Brien-Fleming method and Lan-DeMets alpha spending functions to preserve an overall Type I error rate of 0.05. Thus, the interim analysis will use a significance threshold of $\alpha = 0.006$ (based on 45 patients), and the remaining 0.044 of alpha will be divided evenly between the final analyses of the two primary endpoints.

For futility of the D-dimer endpoint, if the lower limit for the 95% confidence interval of the daily change in D-dimer is above 9% *for the dipyridamole population* at the time of the 50% interim analysis, the trial will be stopped.

It was decided in the December 2020 DSMB meeting to conduct benefit and futility analyses of the composite hierarchical primary endpoint for all patients with study completion as of December 31, 2020. We proceed with the win ratio analysis described above but base futility and benefit decisions on the conditional power approach described in Lan and Trost (1999) and advanced in Siu and Lan (2001) and Lachin (2006). This approach calculates the condition power (CP), defined as the probability of finding a significant result at the end of the study given the interim results and a presumption that the data reflect the true effect size. Decision thresholds are predetermined as:

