- $CP \geq 0.9$: Stop study for benefit
- $0.8 \leq CP < 0.9$: Continue study to planned $N = 127$
- $0.3 \leq CP < 0.8$: Continue study to with re-estimated sample size not to exceed 160
- $CP < 0.3$: Stop study for futility

15.4 *Analysis of Secondary Endpoints*

We will conduct secondary analyses on each component of the hierarchical composite endpoint:

- Time to death
 - *Analysis:* Cox proportional hazards regression
- Number of days on mechanical ventilation during study hospitalization
 - *Analysis:* Poisson regression with subject-level random effects
- Dichotomized (yes/no) decrease in $\text{SpO}_2/\text{FiO}_2$ ratio of at least 50 units relative to baseline at any time during the observation period
 - *Analysis:* Logistic regression
- Cumulative sum of COVID ordinal scores during study hospitalization
 - *Analysis:* Mann-Whitney U-test (nonparametric)

We will analyze an additional secondary endpoint:

- Days free of organ support, where organ support is defined as receipt of invasive or non-invasive mechanical ventilation, high flow nasal oxygen, vasopressor therapy, ECMO support, or COVID-related dialysis, and
- Death at any time is assigned a value of 0 days.
 - *Analysis:* Mann-Whitney U-Test (nonparametric)

Each analysis will include interactions of the study drug by stratification factor.

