6.1 General Study Design and Plan

[figure not shown]
Our primary hypotheses are that patients on dipyridamole will evidence a smaller increase in D-dimer levels and better clinical outcomes on the COVID ordinal score than patients on placebo.

This is a proof-of-concept, placebo-controlled, single-blinded, randomized, 14-day trial of 160 patients.

Participants were assigned treatments to dipyridamole or placebo in 1:1 fashion using stratified, random blocks based on sex and age (above/below 65). Stratified blocks were generated using the ‘blockrand’ package in R.

After randomization, treatment was administered four times daily up until hospital discharge or 14 days, with clinical evaluations made daily. Clinically significant abnormal lab studies were evaluated for relationship to the study drug. Clinical data capture and survival follow-up occurred on Day 28 \pm 1. Patient follow-up occurred again 30 days after last dose of study drug. The study schematic is presented in Figure 1.

Figure 1 Schematic Representation of Study Design

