7.2 Win Ratio Calculations

The standard of care treatment for COVID-19 changed with the introduction of anti-inflammatory steroids, which appear to influence D-dimer concentrations. It was therefore determined to elevate the secondary endpoint to become a co-primary endpoint. This endpoint is a composite of clinical outcomes including death, survival time, mechanical ventilation days, decrease in SpO₂/FiO₂ ratio, and cumulative COVID-19 ordinal scores.

This endpoint will be assessed nonparametrically by comparing outcomes across all possible pairs of treatment-placebo patients and evaluating a 'win ratio' using the Mann-Whitney U-statistic (Pocock et al., 2012). See Section 8.6.2.2 for details. The win proportion is interpreted as the probability that a study drug patient experiences a better outcome than a placebo patient, and in this sense, it represents the effect size for the analysis. We powered our analysis on a presumed 0.67 win proportion (i.e. a patient on study drug is twice as likely to have a better outcome as a patient on placebo). We calculated sample size requirements using the formulas provided in Yosef et al. (2019).

Because we set a 0.006 Type I error significance (alpha) for the interim analysis for benefit of D-dimer, we could only use 0.044 of the original 0.05 for the primary endpoints. We divided the 0.044 between the two co-primary endpoints, leaving a 0.022 two-sided Type I error. Accounting for a 10% dropout, we require 127 patients to have 80% power to significantly detect a win ratio of 0.67.

8 General Analysis Considerations

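### The composite's stop-for-benefit rule at conditional power 0.9 is an efficacy look with no alpha behind it, so the claim that no Type I adjustment is needed holds for the futility branch only

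*SAP*

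**What the plan says.** SAP 8.6.2.2 computes CP under the effect estimated at the interim, for a total of N = 127, and sets four branches: below 0.3, stop for futility; 0.3 to below 0.8, re-estimate the sample size up to 160; 0.8 to below 0.9, continue to 127; 0.9 or more, stop for benefit. It says of the approach that "it does not require an adjustment for the Type I error nor an adjustment on the final critical value to claim significance". Protocol 15.3.1 sets the same thresholds. The Protocol synopsis (Planned Interim Analyses) repeats the Type I part of the claim: "Decisions regarding the secondary endpoint will be based on conditional power, which does not require adjustments for Type I error". The endpoint meant there is the composite, since promoted to co-primary.

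The alpha is fully allotted elsewhere. SAP 7.2 and 10.1 and Protocol 15.3.1 give 0.006 to the D-dimer interim and divide the other 0.044 between the two final tests, "leaving a 0.022 two-sided Type I error" for the composite.

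Other text points towards error control without supplying it. SAP 8.6.2.2 says the interim confidence interval for the win ratio spends the alpha remaining after the D-dimer analysis, but does not link this to the stopping decision. SAP 8.7 claims an overall 0.05 for the primary analyses. Directly after the composite's effect size, Protocol 15.3 says "we will use a P value cutoff of 0.006 for the midway point analysis and 0.044 for the final analysis", without naming the endpoint.

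**The concern.** A futility stop only removes chances to reject. A benefit stop adds one, so it costs Type I error unless the interim has its own alpha or the final critical value is raised. The plan does neither for the composite. SAP 8.7 and 10.2 present 0.022 for the composite, within an overall 0.05, as the level achieved. If the benefit branch had been used at an early look, a co-primary claim could have rested on a result that would have failed the trial's own final threshold.

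**Working it through.** **Inputs**
- Final alpha for the composite: 0.022 two-sided, so 0.011 in the benefit direction; critical Z = 2.290 (SAP 7.2).
- N = 127 from 80% power, win proportion 0.67 and 10% dropout (SAP 7.2), with 1:1 allocation (SAP 6.1).
- CP thresholds 0.3, 0.8 and 0.9 under the current trend (SAP 8.6.2.2).
- Information fraction t = n/127 at the composite interim. **This is an assumption**: only a calendar cut-off of 31 December 2020 is given. SAP 10.2 mentions n = 40, but in a sentence that refers to the D-dimer look. The synopsis caps enrolment at 100, so t lies at or below 100/127 = 0.787.

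**Step 1. Reproduce the plan's own figure.** The Mann-Whitney sample size at 1:1 is N = (2.290 + 0.842)² / [12 × 0.25 × (0.67 − 0.50)²] = 113.1, rounded up to 114. Then 114/0.9 = 126.7, so 127. This matches SAP 7.2 exactly and confirms 0.022 two-sided as the level in use.

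**Step 2. Alpha ledger.** 0.006 + 0.022 + 0.022 = 0.050. Nothing remains for a composite interim test.

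**Step 3. What CP ≥ 0.9 requires.** Under the current trend, CP = Φ[(Z_t/√t − 2.290)/√(1−t)]. So CP ≥ 0.9 means Z_t ≥ √t × (2.290 + 1.2816 × √(1−t)).
At t = 0.5: 0.7071 × (2.290 + 1.2816 × 0.7071) = 0.7071 × 3.196 = 2.26, two-sided p about 0.024. That is weaker than 0.022.

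**Step 4. Type I error of the rule.** In the benefit direction it is P(Z_t ≥ the Step 3 boundary) plus P(trial continues and final Z ≥ 2.290), with Z_t and the final Z bivariate normal with correlation √t under the null.
At t = 0.5 the first term alone is 0.0119, already above 0.011. The second term adds 0.0050 if futility stops are always obeyed, or 0.0078 if they are not. The totals are 0.0169 and 0.0197.

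| t | n of 127 | Z to stop | two-sided p | benefit-direction error, futility obeyed | same, not enforced | two-sided total, not enforced |
|---|---|---|---|---|---|---|
| 0.40 | 51 | 2.08 | 0.038 | 0.0236 | 0.0266 | 0.0376 |
| 0.50 | 64 | 2.26 | 0.024 | 0.0169 | 0.0197 | 0.0307 |
| 0.60 | 76 | 2.40 | 0.016 | 0.0135 | 0.0159 | 0.0269 |
| 0.787 | 100 | 2.56 | 0.011 | 0.0109 | 0.0127 | 0.0237 |
| *planned* | | | | 0.011 | 0.011 | 0.022 |

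A simulation of 4 million null trials at t = 0.5 gave 0.0170 and 0.0197. Re-estimation up to 160 moves the ratio to 0.011 by no more than about 0.05.

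**Step 5. Attribution.** With the benefit branch removed and futility obeyed, the benefit-direction error over these fractions is 0.008 to 0.009, below 0.011. The benefit branch is the cause of the excess.

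**Step 6. Two-sided view with futility obeyed.** Adverse trends are stopped, so lower-tail rejections are below 0.0001 and the total is in effect the benefit-direction column: 0.0236 at t = 0.40, 0.0197 at t = 0.45, 0.0169 at t = 0.50. From about 0.45 upward it is below 0.022.

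**Step 7. An alpha-controlled boundary.** A Lan-DeMets O'Brien-Fleming spend of the composite's 0.022 at t = 0.5 gives a two-sided interim p of about 0.0007 if 0.011 is spent per side, or about 0.0012 if 0.022 is spent in the two-sided form. Either is far below 0.024.

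**The case against.** Four points deserve weight.

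1. *The quoted level is two-sided, and the rule includes the futility stop.* With futility strictly obeyed, the two-sided total stays below 0.022 from a fraction of about 0.45 upward. This stands. The excess is then confined to the benefit direction, where an efficacy claim would be made. With futility not enforced, the total at half information is about 0.031, or 1.4 times 0.022.
2. *The multiple depends on an undocumented fraction.* This also stands. A reader might infer that the error rate was one and a half to two times the planned level. The documents do not support that as a general statement. It describes the 0.011 tail only, for looks at roughly 42% to 58% of 127 depending on how futility is treated. Protocol 15.3.1 speaks of patients with study completion by the cut-off, which suggests a smaller look. SAP 8.6.2.2 speaks of data as of that date, and the footnote to SAP Table 3 censors at data cut-off, which suggests a larger one. At 100 patients the excess is slight or absent.
3. *The look is over and ended in futility.* A reader might infer that a false positive arose, or that the final test is inflated. Neither follows. The synopsis, Protocol 15.1 and SAP 8.1 record a halt for futility, and without a benefit stop the error does not exceed 0.011 in the benefit direction. Rewriting a rule already applied would change no decision.
4. *The 0.006/0.044 sentence in Protocol 15.3 may not concern the composite.* Protocol 15.3.1 ties 0.006 to D-dimer, and 0.044 is not the composite's final level. It may be text from when there was one primary endpoint. Calling it a rival interim rule for the composite is one reading, not a fact.

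None of this rescues the no-adjustment statement as applied to the benefit branch.

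**Conclusion.** The concern holds as a fault in the plan's stated error control. The no-adjustment property is valid for futility and not for stopping for benefit at CP of 0.9 or more, and the 0.05 is fully spent without it. In the benefit direction, against 0.011, the error is about 0.024-0.027 at a fraction of 0.4, 0.017-0.020 at 0.5, 0.013-0.016 at 0.6 and 0.011-0.013 at 0.79; the lower figure assumes futility is always obeyed and the higher that it is not.

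These figures rest on t = n/127, the usual normal approximation for the win statistic, and CP computed under the current trend. The stopping threshold and the empty alpha ledger follow from the documents; the amount of inflation does not, because the interim n is missing.

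**What to change.** 1. In SAP 8.6.2.2 and the Protocol synopsis, limit the no-adjustment statement to futility.
2. In SAP 8.6.2.2 and Protocol 15.3.1, state that the benefit branch at CP 0.9 was not alpha-controlled and did not trigger. Add that any such stop should either be removed or be given a Lan-DeMets O'Brien-Fleming boundary drawn from the composite's 0.022, with the convention named (two-sided p at half information about 0.0007 per side, about 0.0012 two-sided). Present this as a correction of the claim, not as a retrospective change to a rule already applied.
3. In SAP 8.7 and 10.2, report the number of patients at the composite interim, who counted as complete, and the rule's Type I error at that fraction, with futility obeyed and not enforced.
4. Reconcile the synopsis, Protocol 15.3 and 15.3.1, and SAP 8.6.2.2, 8.7 and 10.2 on whether the composite interim spends alpha. Say which endpoint the 0.006/0.044 sentence in Protocol 15.3 governs, and whether the n = 40 in SAP 10.2 has anything to do with the composite.

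Cost: wording and one short calculation. It needs no patients or new data and leaves the final test unchanged. The stated error rate may look somewhat less favourable.

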8.7 Multiple Testing

In the primary analyses, we use the O’Brien-Fleming method to correct for interim analyses and the Lan-DeMets spending function to preserve an overall Type I error rate of 0.05. We will use a Bonferroni adjustment to maintain familywise error for the five secondary analyses. We will not apply a multiple testing adjustment to exploratory endpoints; any findings associated with exploratory endpoints will require confirmation before reporting.

9 Summary of Study Data

Descriptive summary statistics will be tabulated for baseline patient demographics and clinical characteristics separately by intervention group and overall. All tables will be annotated with the total population size relevant to that table (usually the mITT), including missing observations. For continuous variables, the estimated mean, standard deviation, median, minimum, and maximum will be reported. For categorical variables, number and percentages will be reported (excluding missing values).

9.1 Subject Disposition

Patient consent, screening, randomization, degree of study completion (completion of in-hospital follow-up, 28-day follow-up, and 30-day post-drug follow-up), and reasons for dropout will be summarized in a table and a CONSORT diagram. Numbers will be provided by treatment group and overall where appropriate.

[figure not shown]

Figure 2. CONSORT Diagram

9.2 Derived variables

9.2.1 Hierarchical Composite Endpoint Used in Win Ratio Analysis

The win ratio analysis of the hierarchical composite outcome requires a direct comparison of outcomes between each dipyridamole patient and placebo patient. The patient with the superior outcome is adjudicated the ‘winner’ and receives a +1 score, while the ‘loser’ scores -1. The criteria for comparison are below and are summarized in Table 3:

1. If one participant dies and one lives, the participant who does not die wins (Scenario 1)
2. If both participants die, then the participant who lives longer wins (Scenario 2)

3. If both participants die and live the same number of days, then there is a tie (Scenario 3).
4. If neither participant dies, then the participant with fewer days on ventilator wins (Scenario 4).
5. If the participants are tied after step 4, and only one of the participants has a decrease in daily average SpO₂/FiO₂ of 50 or greater, then the participant who does not have the decrease in SpO₂/FiO₂ wins (Scenario 5).
6. If the participants are tied after step 5, then the participant with lower cumulative COVID ordinal score wins (Scenario 6),
7. If the participants are tied after step 6, then their final result is a tie (Scenario 7).

Table 3. Description of Hierarchical Composite Endpoint Win Scenarios

Scenario	Death [1]	Survival [1]	Number of days on mechanical ventilation [2]	Decrease from baseline in SpO ₂ /FiO ₂ \geq 50 [3]	Sum of COVID ordinal scores [4]	Score
1	Dead					-1
	Alive					+1
2	Dead	Shorter				-1
	Dead	Longer				+1
3	Dead	Tied				0
	Dead	Tied				0
4	Alive	N/A	Longer			-1
	Alive	N/A	Shorter or None			+1
5	Alive	N/A	Tied	Yes		-1
	Alive	N/A	Tied	No		+1
6	Alive	N/A	Tied	Tied	Higher	-1
	Alive	N/A	Tied	Tied	Lower	+1
7	Alive	N/A	Tied	Tied	Tied	0
	Alive	N/A	Tied	Tied	Tied	0

[1] Death and survival are assessed from the time of study medication to 30 days after the last dose of study drug (a maximum of 44 days from consent). Participants are censored at the time of drop-out or the data cutoff date (if no event has occurred).
 
[2] Number of days on mechanical ventilation are counted from the time of study medication until hospital discharge. If a participant is re-hospitalized and receives ventilation, these data are not counted.
 
[3] Oxygenation measurements are collected from EHR records. Baseline is defined as the average of measurements taken between 8 hours prior to start of study medication and the start of study medication administration. A 50-point drop is defined as a participant who experiences two consecutive measures of at least 50 points below baseline. Post-baseline measurements are assessed up to and including day 44 (from consent).
 
[4] COVID ordinal scores are defined in Table 2.
						

The cumulative sum of COVID ordinal scores used in Step 6 is calculated as the time-weighted sum of daily ordinal scores, with units of ordinal score days. For example, if a subject started medication at 9:00 pm on Day 1 with a score of 4, and that score decreased to 3 at 6:00 am the next day, and that patient was discharged at noon on the third day, then the cumulative sum of ordinal scores would be:

$$\frac{\{3 \text{ hrs} \times 4 + (6 \text{ hrs} \times 4 + 18 \text{ hrs} \times 3) + 12 \text{ hrs} \times 3\}}{24 \text{ hrs/day}} = \frac{12 + (24 + 54) + 36}{24} = 5.25$$

The use of the cumulative ordinal score in Step 6 of the above algorithm is meant as a combined measure of the severity and duration of a patient's illness, since longer hospitalizations and larger daily ordinal scores will both increase the cumulative total.

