3 STUDY OUTCOMES

3.1 Primary Outcome

1. **Title:** D-dimer

Description: Change in plasma D-dimer level compared with baseline at enrollment

Time Frame: Data gathered through day 14

2. **Title:** Hierarchical composite rank score

Description: Hierarchical composite rank score of death, days on ventilation, decline in daily average SpO₂/FiO₂ of 50 or more compared to enrollment, cumulative COVID ordinal score

Time Frame: Data gathered through 28 ± 1 day

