8.4.3 Administration Instructions

The pharmacy will dispense study drug after randomization has been completed. The medical team will administer the study drug four times per day in both study groups (dipyridamole 100

mg QID, placebo QID). If a participant is discharged during the 14-day treatment period, the study drug will be disposed of per local institute policy.

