5.2 Endpoints

For convenience, we give names to the following times and time windows:

- Baseline or Day 1: Date of the first study drug administration
- Study Hospitalization: Day 1 through either Day 14 or hospital discharge, whichever is first
- Observation Period: The 28-day period following first study drug administration
- Study Duration: The period from baseline until 30 days after last study drug administration

If an endpoint is to be evaluated at all three of the above time points, we use the phrase ‘at any time point’.

Endpoints are presented in a numbered list to facilitate references to endpoints when conducting the final analysis.

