5.2.1 Primary Endpoint

The first co-primary endpoint is increase in plasma D-dimer levels compared to baseline.

The second co-primary endpoint is a clinical hierarchical composite of:

- Time to death from any cause during study duration
- Number of days on mechanical ventilation during study hospitalization
- A dichotomized (yes/no) decrease in daily average SpO₂/FiO₂ ratio of at least 50 units relative to Day 1 at any time during the observation period
- Cumulative sum of COVID ordinal scores during study hospitalization

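### The death tier of the composite co-primary has two conflicting windows, and one of them ends on a day set by when each patient's drug stopped

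*SAP*

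**What the plan says.** **Fixed window.** For the composite, Protocol 3.1 (item 2) states: "Time Frame: Data gathered through 28 ± 1 day". Protocol 3.2 sets the same limit for days to mortality. SAP 6.1 reports that "Clinical data capture and survival follow-up occurred on Day 28", with a one-day tolerance.

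**Last-dose window.** SAP 5.2.1 makes the first component "Time to death from any cause during study duration", and SAP 5.2 defines the term: "Study Duration: The period from baseline until 30 days after last study drug administration". Table 3, note [1], in SAP 9.2.1 repeats it: "Death and survival are assessed from the time of study medication to 30 days after the last dose of study drug", with "a maximum of 44 days from consent". Protocol 15.3 also ties the death component to study duration.

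**A fixed window the SAP defines but does not use for death.** SAP 5.2: "Observation Period: The 28-day period following first study drug administration". SAP 5.2.1 applies it to the SpO₂/FiO₂ tier, although Table 3, note [3], runs that tier to day 44.

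**When drug stops.** SAP 6.1 has treatment end at discharge or at 14 days. Protocol 8.4.3 is consistent with this: "If a participant is discharged during the 14-day treatment period, the study drug will be disposed of per local institute policy". Protocol 12.1 adds withdrawal of consent, adverse events and protocol violations. SAP 8.4 notes that, in preliminary results, most patients left hospital early.

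**The concern.** There are two problems.

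First, the highest-priority tier of a co-primary endpoint has two definitions in approved text. Two programmers could treat a death after Day 28 differently, and each could cite a section in support.

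Second, the last-dose definition gives patients follow-up of different lengths, and the length is decided after randomisation by discharge, intolerance or withdrawal. Treatment may affect any of these. The win steps in SAP 9.2.1 ask only who died and who lived. Note [1] censors at drop-out or data cutoff, but no step says how to compare two patients whose windows end on different days. If one arm stopped drug sooner, fewer of its late deaths could count, with no difference in survival.

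**Working it through.** **1. The plan's own figures.**

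- Longest window: last dose on Day 14, and 14 + 30 = Day 44. This matches the stated maximum of 44.
- Sample size (SAP 7.2): win proportion 0.67, 80% power, 10% dropout, two-sided alpha (0.05 − 0.006)/2 = 0.022. The SAP cites a published formula that it does not print. The Noether formula for a 1:1 Mann-Whitney test gives N = (z₀.₉₈₉ + z₀.₈₀)² / [12 × 0.25 × (0.67 − 0.5)²] = 113.1, rounded up to 114. Then 114/0.90 = 126.7, which rounds up to the stated 127. The length of follow-up does not enter this formula, so changing the death window leaves 127 as it is.

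**2. End of the death window, by day of last dose (last dose + 30).**

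| Last dose | Window ends | Days past Day 28 |
|---|---|---|
| Day 1 | Day 31 | 3 |
| Day 3 | Day 33 | 5 |
| Day 5 | Day 35 | 7 |
| Day 7 | Day 37 | 9 |
| Day 10 | Day 40 | 12 |
| Day 14 | Day 44 | 16 |

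The spread is 44 − 31 = 13 days. Every window passes Day 28. Deaths to Day 31 fall inside everyone's window, so only deaths from about Day 32 to Day 44 depend on the stop day. The conflict with Protocol 3.1 and 3.2 is slightly wider and covers deaths from about Day 29 to Day 44.

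**3. Two patients who both die on Day 38.** With last dose on Day 14, the window ends on Day 44 and the patient is dead. With last dose on Day 4, it ends on Day 34 and the patient is alive. The second patient beats the first on the death tier, although they died on the same day. A rule limiting the pair to their shared 34 days would tie them on death and pass them to the ventilator tier, but the SAP has no such rule.

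**4. Largest effect of one reclassified death.** Assume the 100 enrolled split 50 and 50, and ignore stratification. One patient enters 50 of the 50 × 50 = 2,500 pairs. Moving from losing all of them to winning all of them shifts the win proportion by 50/2,500 = 1/50 = 0.02. The null standard error is √[(2n + 1)/(12n²)] with n = 50, that is √(101/30,000) = 0.058, so the ceiling is 0.02/0.058 = 0.34 standard errors. At 127 patients the ceiling is 1/63.5 = 0.016. The actual shift is smaller for a patient who would lose most pairs on ventilator days anyway.

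**5. Expected shift with no true effect.** These inputs are assumptions, not taken from the documents. Let q be the risk of a late death, the same in both arms, and let t and c be the shares of the treated and control arms whose window is long enough to count it. Splitting all other pairs evenly, the expected win proportion is 0.5 + q(c − t)/2.

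- q = 1%, t = 20%, c = 30%: 0.5 + 0.01 × 0.10/2 = 0.5005.
- q = 5%, t = 20%, c = 40%: 0.5 + 0.05 × 0.20/2 = 0.505.

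Against the planned effect of 0.67 − 0.50 = 0.17, these are 0.0005/0.17 = 0.3% and 0.005/0.17 = 2.9%.

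**The case against.** The strongest reply is that the SAP is not departing from the protocol. Protocol 15.3, the protocol's own analysis section, uses study duration, and Protocol 15 lets the SAP modify the plan. That stands. A reader might infer that the SAP overrides a protocol that is settled on Day 28, and the documents do not support this: the protocol disagrees with itself, and the SAP follows one side. The need to reconcile the sections remains.

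Second, the exposure is narrow, and bias between arms also needs the stop days to differ between arms. That stands too, and it limits the size. It does not supply the missing pairwise rule.

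Third, Cox risk sets accommodate unequal follow-up, so the secondary analysis of death would be biased only if censoring after Day 31 were informative. This is fair. The link between discharge and prognosis makes informative censoring possible, but the documents do not allow it to be measured.

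Fourth, the planned participant call comes 30 days after last dose, and the Day 28 contact in the SAP's schedule of events is a chart review. A reader should therefore not infer that survival status at Day 28 is known to have been obtained for everyone. It was planned then, and the later call would normally settle it.

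Fifth, a reader might want every endpoint that uses study duration moved to Day 28. For readmission this would do harm. In patients dosed until discharge, last dose + 30 gives about 30 days at risk after leaving hospital. A Day 28 limit would give 28 − 4 = 24 days after a Day 4 discharge but 28 − 14 = 14 days after a Day 14 discharge.

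**Conclusion.** The point holds in a limited form. The death tier has conflicting windows across Protocol 3.1, 3.2 and 15.3 and SAP 5.2, 5.2.1 and Table 3, note [1]. The last-dose version depends on an event after randomisation, with no rule for pairs with unequal follow-up. It should be corrected because the definition is ambiguous at the top of a co-primary, not because a large bias has been shown.

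The likely effect is small. The 0.02 ceiling per death assumes 50 per arm and an unstratified analysis, whereas the final analysis is stratified. The range of about 0.0005 to 0.005 rests on assumed late-death risks and assumed differences in stop days. A reader might infer that the result is biased towards one arm. The documents give neither the number of deaths from Day 32 to Day 44 nor the stop days by arm, so neither the presence nor the direction of bias can be stated.

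**What to change.** - Reconcile Protocol 3.1, 3.2 and 15.3 with SAP 5.2, 5.2.1, 10.3 and Table 3, note [1], so that death is counted through one fixed day from first dose for every participant, in the win algorithm and in the Cox analysis. Day 28 is the natural choice: Protocol 3.1 and 3.2 already state it, survival follow-up was planned then, and every last-dose window extends past it. Apply the cut to the date of death, so that the one-day visit tolerance does not matter.
- Align the SpO₂/FiO₂ tier to the same window, resolving day 44 in Table 3, note [3], against the 28-day period in SAP 5.2.1. Otherwise a patient who dies on Day 35 could rank as alive and still be scored on oxygenation after Day 28.
- In SAP 8.4, make clear that death is not censored at discharge. Read literally, its sentence on time-to-event responses would do that.
- Keep the last-dose + 30 rule, which the SAP also attaches to the interim analysis, as a sensitivity analysis. Report deaths after Day 28 descriptively by arm.
- Record the change and its date. Settle it without reference to late deaths by arm.
- Leave the readmission window and the period for collecting serious adverse events as they are.

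The cost is wording only, with no new data collection and no change to N = 127. There are two drawbacks. Deaths after Day 28 leave the primary comparison. The final definition would also differ from the interim one, although SAP 10.2 says the two analyses differ only in stratification, so that sentence needs amending as well.
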